## 2 INTRODUCTION

The Transthyretin-Associated Amyloidosis Outcomes Survey (THAOS) is a non-interventional, global, multi-center, longitudinal, observational survey open to all patients with Transthyretin (ATTR) amyloidosis, including both due to TTR variants (ATTRv) and wild-type forms of the disease (ATTRwt), and patients with TTR gene variants (previously referred as mutations) without disease diagnosis. At the inception of THAOS, limited data were available on the natural history of the ATTRv and ATTRwt forms of the disease, including the regional differences in disease expression by TTR variants and non-mutated TTR, and the genotypic-phenotypic relationship in ATTR.

The objectives of THAOS are to describe the population of patients affected with ATTR amyloidosis and to enhance the understanding of the disease natural history, including the variability and progression of the hereditary and acquired forms of disease by studying a large and heterogeneous patient population. Survey data may be used to develop new treatment guidelines and recommendations, and to inform and educate clinicians about the management of this disease.

The survey can also generate descriptive safety summaries using adverse events (AE) and serious adverse events (SAE) data in tafamidis-treated patients. AE/SAE data collection in THAOS will be utilized in the post-marketing setting to provide additional information on the safety of tafamidis over the longer term as well as its effect on survival. Additionally, the collection of safety data in THAOS will fulfill part of the post-marketing commitment to the Committee for Medicinal Products for Human Use

PFIZER CONFIDENTIAL

(CHMP) for tafamidis. Specifically, this non-interventional (NI) study is designated as a Post-Authorization Safety Study (PASS) and is a commitment to the European Medicine Agency (EMA).

The objectives of THAOS are to describe the population of patients affected with ATTR amyloidosis and to enhance the understanding of the natural history of ATTR amyloidosis, including the variability and progression of the hereditary and acquired forms of disease.

The purpose of this statistical analysis plan (SAP) is to support a final study report. Separate statistical analysis plans will be provided for other efforts including but not limited to annual reporting for regulatory requirements, to facilitate reimbursement discussions, and for abstract and/or publication development. Additionally, a separate SAP is available for the B3461029 substudy to evaluate safety and efficacy in transthyretin amyloid polyneuropathy (ATTR-PN) patients with variants other than substitution of methionine for valine at position 30 (Val30Met).

## 2.1 STUDY DESIGN

THAOS is a non-interventional, global, multi-center, longitudinal observational survey open to all patients with ATTR amyloidosis, including both inherited and wild-type forms of disease, and patients with TTR gene variants without disease diagnosis. There is no set number of patients to be enrolled. The study has been open since 2007 and will continue until Pfizer declares the study complete (currently estimated to be the year 2023) or as long as patients are able to participate, or until they withdraw consent.

THAOS does not involve the administration of an investigational agent or other interventions. Patients will continue to receive their current medications and all other standard care for their disease. It is recommended that assessments be conducted at least annually and be recorded in the THAOS electronic data record close to the time they are performed.

Treatment with tafamidis or with other disease modifying therapies will be according to the product label with commercially available product or according to protocol-specified requirements if a patient is enrolled in a separate tafamidis interventional study while simultaneously being followed in THAOS.

In addition to routine procedures for standard of care, patients will be asked to complete patient outcome questionnaires at least annually; these are optional and do not affect eligibility to participate in the survey.

### **Study population**

The THAOS study population includes enrolled patients with confirmed ATTRh or ATTRwt amyloidosis and those with a TTR gene variant without a diagnosis of ATTR amyloidosis.

TTR genotyping is required to confirm eligibility and will be performed before the Eligibility/Baseline visit and outside of the auspices of the survey according to the site's standard practices. For patients with a documented TTR variant, the variant(s) is recorded in the patient's medical record.

### Assessments

A series of assessments will be used to assess disease progression and the effects of tafamidis treatment including demographics, TTR genetic test results, tissue biopsy results, family disease history, medical history, annual medical assessment, general examination, concomitant medication use, hospitalizations, transplant history and complications related to transplantations, AE/SAE reporting for tafamidis-treated patients, health events of interest, clinical laboratory data, urinalysis, CCI [REDACTED], [REDACTED] neurologic assessments, eye examination, body composition, CCI [REDACTED], [REDACTED] and death.

Data will be collected at an eligibility/baseline visit, return visits, and in the form of status updates if the patient has not visited the site. In addition, pre-baseline retrospective data may optionally be captured.

Return visits will be conducted annually (on average) or at the discretion of the survey physician. The reporting window for collecting changes in signs, symptoms, AEs, and new diagnoses is from the last prior visit.

A final visit, including collection of AE/SAE information will be performed at the completion of the survey or at the time the patient elects to discontinue, whichever occurs first. For patients enrolled in interventional clinical trials that include open-label tafamidis or other open label investigational products, follow-up in THAOS may continue, but AE data collection and reporting will be addressed through the interventional clinical trial sponsor. If a patient dies while enrolled in the survey, the site is asked to collect all available information related to the death.

If a patient enrolls in a double blind investigational clinical trial or any other trial (including Tafamidis Compassionate Use/Early Access Program) during the course of their follow-up in THAOS, data collected for such patients (if included in the THAOS database) will be excluded from analyses specified within this SAP.

AE/SAE data collected in THAOS will be used to further characterize the safety profile of tafamidis and as a result, to fulfil certain aspects of the European Union (EU) post-

marking commitment for tafamidis. Based on the safety concerns detailed in Table 1, corresponding data for Health Events of Interest will be summarized to characterize both the natural history of ATTR amyloidosis in participants not treated with tafamidis and safety concerns amongst tafamidis-treated patients.

**Table 1 Summary of ongoing tafamidis safety concerns to be addressed in THAOS**

Level of Risk or Missing Information	Specific Concerns
Important potential risks	Hepatotoxicity Reproductive and developmental toxicity and lactation Changes in thyroid function, particularly in pregnant women
Important missing information	Safety and efficacy in patients with ATTR-PN variants other than Val30Met (B3461029 substudy) CCI █ Patients with severe hepatic impairment

Note: The important identified risks (Urinary tract infections, Diarrhea, Upper abdominal pain and Vaginal infections); important potential risks (Hypersensitivity reactions); and missing information (Safety and efficacy in elderly patients and Longer-term safety) have been removed from the list of ongoing safety concerns from the tafamidis EU Risk Management Plan (RMP) Update (v 9.3), approved on 17 February 2020 and therefore will not be addressed in the final clinical study report (CSR) for THAOS.

All AE/SAE data will be collected for patients treated with commercially available tafamidis; patients receiving tafamidis as part of their participation in an open-label clinical study will have AE/SAE data collection through the open-label clinical study; reporting of Health Events of Interest will be available for patients not treated with tafamidis.

All visits are intended to be outpatient visits. Table 2 presents the data collected throughout a patient's participation in THAOS per the case report form (CRF). All assessments listed in Table 2 are recommended, but not required and will be determined by the investigator.

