## **7.2. Rationale for the Survey**

The Transthyretin Amyloidosis Outcomes Survey (THAOS) is a longitudinal, observational survey open to all patients with TTR gene mutations without a diagnosis of ATTR amyloidosis and to patients diagnosed with ATTR amyloidosis (inclusive of ATTR-PN and ATTR-CM). To date, limited data are available on the natural history of the hereditary (ATTRm) and wild-type (ATTRwt) forms of the disease, including the regional differences in disease expression by TTR variants and non-mutated TTR, and the genotypic-phenotypic relationship in ATTR amyloidosis.

The principal aims of the outcome survey are to better understand and characterize the natural history of the disease by studying a large and heterogeneous patient population. Survey data may be used to develop new treatment guidelines and recommendations, and to inform and educate clinicians about the management of this disease.

The survey can also generate descriptive safety summaries using adverse and serious adverse event (AE/SAE) data in tafamidis-treated participants. All AE/SAE data will be collected and summarized, including (but not limited to) the safety concerns detailed in [Table 1](#), Summary of Safety Concerns to be Assessed in THAOS.

AE/SAE data collection in THAOS will be utilized in the post-marketing setting to provide additional information on the safety of tafamidis over the long term as well as its effect on survival.

Limited data was collected in ATTR-CM studies with tafamidis in patients with New York Heart Association (NYHA) class IV, and it is expected that THAOS will provide additional information on the safety and efficacy of tafamidis in this population. Safety data will be collected through THAOS for all participants treated with tafamidis.

Additional data corresponding to the events of interest detailed in [Table 1 Summary of Safety Concerns to be Assessed in THAOS](#) will also be collected for all THAOS participants (tafamidis-treated and participants not treated with tafamidis). The purpose of the additional data collection is to further characterize the natural history of disease amongst untreated participants and, as applicable, to gather data to provide context for safety events observed amongst tafamidis-treated participants.

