**Table 1. \*Summary of Safety Concerns to be Assessed in THAOS**

Important identified risks (Adverse Drug Reactions)	Urinary tract infection Diarrhea Vaginal infections Upper abdominal pain
Important potential risks	Hepatotoxicity Hypersensitivity reactions Reproductive and developmental toxicity and lactation Changes in thyroid function, particularly in pregnant women
Important missing information	Safety and efficacy in elderly patients Longer term safety Safety and efficacy in patients with ATTR-PN mutations other than Val30Met Patients with NYHA Class IV Patients with severe hepatic impairment

Note: \*The following important identified risks (Urinary tract infections, Diarrhea, Upper abdominal pain and Vaginal infections); important potential risks (Hypersensitivity reactions); and missing information (Safety and efficacy in elderly patients and Longer-term safety) have been removed from the list of ongoing safety concerns from the tafamidis EU RMP Update (v 9.3), approved on 17 February 2020.

All AE/SAE data will be collected for participants treated with commercially available tafamidis; participants receiving tafamidis as part of their participation in an open-label clinical study will have AE/SAE data collection through the open-label clinical study; reporting of other events in addition to the Events of Interest will be available for participants not treated with tafamidis.

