## 2.2 STUDY OBJECTIVES

The objectives of THAOS are to:

- Describe the population of patients affected with ATTR amyloidoses;
- Enhance the understanding of disease natural history, including the variability and progression of the hereditary and acquired forms of the disease;
- Better understand the genotype – phenotype relationship in ATTRv;
- Compare the progression of disease and overall survival in patients with ATTR amyloidosis with and without liver transplant;
- Foster an international community of medical experts who will develop recommendations on the clinical management of ATTR amyloidoses;
- Provide information to better understand the management and treatment of patients with ATTR amyloidoses through publication of the survey data;
- Provide information on off-label use of tafamidis by identifying patients who do not meet the inclusion criteria for transthyretin amyloid cardiomyopathy (ATTR-CM)
- For tafamidis-treated patients, collect and summarize all AE/SAE data, including for the specific safety concerns outlined in Table 1 Summary of Safety Concerns to be Assessed in THAOS comprising important identified risks, important potential risks, and missing information that includes long-term safety in ATTR-CM patients with **CCI** [REDACTED] Class IV.
- For patients not treated with tafamidis, collect and summarize additional data on the events of interest listed in Table 1.

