### **Exposure**

Duration of exposure (in years) among patients receiving tafamidis while enrolled in THAOS will be summarized (excluding time when the patient was part of clinical trial or Compassionate Use/Early Access Program) by starting dose using the tafamidis treated set by phenotype at enrollment and overall, CCI [REDACTED] and either predominantly cardiac or mixed phenotype at enrollment, tafamidis treated set for patients who had severe hepatic impairment at baseline, tafamidis treated set by liver transplantation status (liver transplant prior to first dose of tafamidis/liver transplant after the first dose of tafamidis/no liver transplant).

Additionally the duration of treatment with 20 mg and 61 mg/80 mg will be summarized separately for patients with off label use.

The duration of exposure (in years) will be calculated as:

Sum of all non-missing days when tafamidis was taken (excluding days of other clinical trial/compassionate use participation) / 365.25

Summary of exposure-adjusted Incidence rates (per patient-year) AEs and SAE for Treatment Emergent Adverse events (All causalities) and mortality for tafamidis treated set will be provided.

A separate listing will be provided for duration of exposure listing for patients who switched from 61/80 mg to 20 mg.

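### The SAP Table 1 note excludes longer-term safety and the removed risks from the final report, in conflict with SAP 2, 2.2 and 6.2, and the AE/SAE outputs are not split by time on tafamidis

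*SAP*

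**What the plan says.** The note under SAP Table 1 begins with "The important identified risks (Urinary tract infections, Diarrhea, Upper abdominal pain and Vaginal infections", goes on to hypersensitivity, and states that "missing information (Safety and efficacy in elderly patients and Longer-term safety) have been removed from the list of ongoing safety concerns". It ends by saying that the RMP update was "approved on 17 February 2020 and therefore will not be addressed in the final clinical study report (CSR) for THAOS". The table itself has rows only for potential risks and missing information.

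Elsewhere the SAP points the other way:

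- Section 2 says that the AE/SAE data will be "utilized in the post-marketing setting to provide additional information on the safety of tafamidis over the longer term". Protocol 7.2 says the same: "provide additional information on the safety of tafamidis over the long term as well as its effect on survival".
- Section 2.2 keeps as an objective the AE/SAE summary of the Table 1 concerns, "comprising important identified risks, important potential risks, and missing information that includes long-term safety in ATTR-CM patients" in Class IV.
- Section 6.2 commits to summarizing all AE/SAE data, with the Table 1 concerns as one part of that.

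For the analysis, SAP 8.2.6 (Exposure) plans a "Summary of exposure-adjusted Incidence rates (per patient-year) AEs and SAE for Treatment Emergent Adverse events (All causalities") and mortality, for the treated set. SAP 8.2.6 (Adverse Events & Serious Adverse Events) breaks AEs down by severity, starting dose, phenotype and subgroup. It gives grouped-term tables for hepatotoxicity, reproductive toxicity, thyroid function and off-label use.

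**The concern.** The SAP exists to support the final report of a post-authorization safety study. Its note rules out of that report a topic that its introduction names as a use of the safety data. A programmer or report author could follow either statement.

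The AE/SAE plan does not settle the matter. Labs, blood pressure and ECG are shown by yearly interval and mortality by Kaplan-Meier, but AE and SAE rates have no time axis. A rate per patient-year describes long-term safety fully only if the rate is constant over years on drug. If it changes, early person-time carries most of the weight and the change is diluted. The report would then have little to say on AE rates in later years of treatment, although the dates needed are collected.

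**Working it through.** **Text side by side**

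| Place | Longer-term safety | Identified risks |
|---|---|---|
| SAP Table 1 note | not addressed in final report | not addressed in final report |
| SAP 2 | a use of the AE/SAE data | not mentioned |
| SAP 2.2 | Class IV ATTR-CM only | part of the objective, by reference to Table 1 |
| SAP Table 1 rows | no general row | no row |
| SAP 6.2 | all AE/SAE data summarized | all AE/SAE data summarized |
| Protocol Table 1 | listed, footnoted as removed from RMP | listed, footnoted as removed from RMP |

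SAP 2 conflicts with the note on longer-term safety, and SAP 2.2 refers to a category that SAP Table 1 no longer contains. SAP 6.2 is compatible with the note only if not addressed means no dedicated output.

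**Time on drug.** SAP 8.2.6 defines one summed exposure duration per patient. The AE/SAE row of SAP 8.2.8 has no readable column for time since first dose.

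**Size of the dilution.** The plan has no figure to reproduce: it gives no sample size, event rate or exposure distribution. From the documents:

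- EU approval 16 November 2011 (Protocol 7.1) to last visit 16 June 2023 (Protocol 6): T = 11.58 years.
- Earliest ATTR-CM approval cited, March 2019 (Protocol 7.1), to the same date: about 4.25 years.

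Let w be the share of person-time after year 5 and RR the factor by which the event rate rises then. The pooled rate, relative to a constant rate, is (1 − w) + RR·w = 1 + (RR − 1)·w. Everything below is assumed.

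Model A: exponential time on drug with mean m, cut off at T, all starting together. Then w = (e^(−5/m) − e^(−T/m)) / (1 − e^(−T/m)). For m = 3: (0.1889 − 0.0211) / (1 − 0.0211) = 0.171.

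Model B: starts spread evenly over the 11.58 years, discontinuation hazard h per year. Person-time at time t is proportional to e^(−ht)(1 − t/T), integrated numerically.

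| Assumption | w after year 5 | Pooled ratio, RR = 2 | Pooled ratio, RR = 3 |
|---|---|---|---|
| A, m = 2 | 0.079 | 1.08 | 1.16 |
| A, m = 3 | 0.171 | 1.17 | 1.34 |
| A, m = 5 | 0.299 | 1.30 | 1.60 |
| B, h = 0.30 | 0.099 | 1.10 | 1.20 |
| B, h = 0.20 | 0.152 | 1.15 | 1.30 |
| B, h = 0.10 | 0.226 | 1.23 | 1.45 |
| B, h = 0.05 | 0.272 | 1.27 | 1.54 |

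If the change comes after year 3, Model B gives 1.27 to 1.49 for a doubling.

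The pooled rate also cannot separate patterns. With h = 0.10, 0.5 per 100 patient-years early and 2.71 after year 5 gives 0.774 × 0.5 + 0.226 × 2.71 = 1.00, the same as a flat rate of 1.0.

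**What a split would show.** Assume 1,000 patients, h = 0.10, and rates of 1.0 early and 2.0 late per 100 patient-years. There are 4,077 patient-years, 921 of them late, with 31.6 early and 18.4 late events. The pooled rate is 50.0/4,077 = 1.23 per 100 (95% CI 0.93 to 1.62). Split, the late rate is 2.0, with CI 2.0 × e^(±1.96/√18.4) = 1.27 to 3.16. The split shows the pattern, with a wide late interval.

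**The case against.** The strongest answer is that the note only closes RMP items. It sits under a table of ongoing concerns, it gives its reason, and Protocol Table 1 carries a footnote recording the same removal. Protocol 9.7.1 lets the SAP modify protocol plans. This stands: the change is not a fault in itself. What it does not explain is why SAP 2 and 2.2 were left unreconciled with it.

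A reader might infer that urinary tract infection, diarrhea and the other removed items vanish from the report. The documents do not support that: SAP 6.2 and 8.2.6 summarize all AEs and list AEs for all enrolled patients. A reader might also infer that the Class IV long-term objective was dropped. The removal note does not name Class IV, and parts of SAP Table 1 and of the subgroup columns in SAP 8.2.8 are redacted, so nothing visible drops it.

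The safety plan is not blind to time, given its yearly and Kaplan-Meier outputs and the annual RMP safety analyses under separate plans. The gap is AE/SAE rates in this report. The rates may also be shown by dose group, since the Amendment 2 rationale cites differing exposure between dose groups, but that is not a split by time.

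Finally, a rising rate would not by itself show a drug effect. Protocol 11.4.1 counts worsening of the underlying disease as an AE, and late bands hold only patients who survived and stayed on treatment. This stands as a limit on interpretation.

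**Conclusion.** The point holds in limited form. The SAP's statements on longer-term safety and identified risks do not agree and should be reconciled. Separately, the readable AE/SAE outputs cannot show whether rates change with years on tafamidis.

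Under the assumed exposure patterns, a doubling after year 5 raises the pooled rate by about 8% to 30%, and a tripling by about 16% to 60%. These figures rest on assumed exposure, change point and rate ratio, none of which the documents give. It would be tempting to say that a late harm is averaged away. The figures show dilution, and a large late effect would still move the pooled rate. Redacted sections could not be checked.

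A dedicated grouped table for the closed RMP items is a matter of preference, because the documents give a reason for closing them.

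**What to change.** 1. **Reconcile the SAP text.** Bring the Table 1 note into line with sections 2, 2.2 and 6.2. For example, say that the removed items are no longer ongoing RMP concerns and get no dedicated output, but are covered in the overall AE/SAE summaries. Align the reference to identified risks in 2.2 with the rows of SAP Table 1.

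2. **Add a time split in SAP 8.2.6.** Give descriptive exposure-adjusted AE and SAE rates for the treated set by time since first tafamidis dose, for example under 1, 1 to under 3, 3 to under 5, and 5 or more years.
   - Patients already on drug at enrollment enter at their actual time since first dose. The study day in SAP Appendix 2 does not give this, because for them it can run from consent.
   - Only person-time within THAOS goes into the denominator.
   - State whether excluded trial or compassionate-use time counts toward time since first dose.
   - Use shorter bands for the Class IV cardiac subset. With about 4.25 years from the earliest ATTR-CM approval cited to last visit, a band of 5 years or more would be empty under labelled ATTR-CM use.
   - State that rates across bands may reflect disease progression and selection, and are to be read descriptively.

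**Cost.** A wording change and a few tables. SAP Table 2 already logs tafamidis start and stop dates, so no new data collection or hypothesis test is needed. Late bands will be imprecise, most of all in small subgroups, where the SAP rule of at least 10 patients for descriptive statistics still applies.
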